## Abstract

**Objective:** To determine if there is less pain from a corticosteroid injection with or without lidocaine with epinephrine when pharmacologically treating trigger finger (stenosis tenosynovitis).

**Research Plan:** The treatment of trigger finger involves an injection of corticosteroid (e.g., 40 mg Kenalog). Kenalog treats the underlying inflammatory pathology. Some surgeons add lidocaine with epinephrine as a local anesthetic with the injection. Lidocaine with epinephrine is associated with a burning sensation and may be the primary pain associated with the injection. We hypothesize that a corticosteroid injection without lidocaine with epinephrine will be less painful, and equally effective in treating trigger finger. This hypothesis is based on experience injecting without lidocaine with epinephrine (i.e., Kenalog only) in clinic. Comparison of these two methods has not been done previously. Patients presenting to our clinic with trigger finger will have the option to electively enroll in this study comparing the two methods.

**Methods:** Patients will be randomized into two groups with randomizing software. The two groups will include (1) 1mL corticosteroid + 1mL Lidocaine with epinephrine vs (2) 1mL corticosteroid + 1mL saline. The surgeon (injector) will also be blinded to the selected treatment to avoid bias. The pain levels will be assessed at 1 minute after the injection using the VAS pain scale.

## 1. Introduction

Trigger finger is a pathology of the flexor tendons in the fingers. Under normal physiologic conditions, the flexor tendon slides under a close-fitting tendon sheath when the finger extends or flexes. However, in some patients, the flexor tendon can become irritated and subsequently develop inflammatory nodules. When this happens, the nodules catch the tendon sheath during finger extension and flexion. This can cause pain and dysfunction.

The treatment for trigger finger involves the injection of a corticosteroid to shrink the inflammatory nodule on the flexor tendon. Often, the injection involves a 50:50 mixture of local anesthetic and corticosteroids. The lidocaine with epinephrine component of the injection causes a burning sensation, which causes discomfort during the procedure. Lidocaine with epinephrine is not anti-inflammatory and does not treat the underlying pathology. To date, there are no formal studies that have compared the pain outcomes and long-term efficacy of using corticosteroids + lidocaine with epinephrine vs corticosteroid injections alone.

Trigger finger is present in 3-5% of the general adult population, and up to 10% of diabetic patients. This project hopes to establish a treatment method that is less painful and involves fewer medications without sacrificing long-term efficacy. If this project yields significant results, it could change the practice of trigger injections on the national level, this would impact millions of patients.

## 2. Objective and hypothesis

The purpose of this study is to see if removing lidocaine with epinephrine from trigger finger injections decreases pain of the shot without decreasing the effectiveness of the treatment. We hypothesize that using an injection of corticosteroids (without lidocaine with epinephrine) will reduce the need for treatment.

## 3. Study Procedures

### 3.1 Study Design

This study will be a prospective randomized control trial. The study will also be double blind, as the patient and physician will not know which injection is being used. Both interventions (Kenalog + Lidocaine with epinephrine and Kenalog alone) can be classified as standard of care, as they are already being used in our clinic and by surgeons around the world in a similar fashion.

Syringes will be pre-filled by the study personnel with either:

1. 1mL 1% lidocaine with epinephrine with epinephrine and 1ml of Kenalog 40 (2 mL total)

2. 1mL of 0.9% saline and 1ml of Kenalog 40 (2 mL total)

Patients will have an equal (50% chance) of receiving either injection that will be determined by using randomizer software.

### **3.2 Data points**

We will keep track of the following:

- Patient identification (medical record number)
- Age
- Gender
- Type of Injection
- Date of injection
- Digit/Hand
- Reported Pain Score at 1 minute
- Adverse effects of injection (infection, skin pigmentation, atrophy)

We will also be keeping track of the following comorbid conditions to better analyze our data:

- Diabetes (insulin dependent, non-insulin dependent)
- Hypothyroidism
- Chronic opioid use
- Smoking history
- Carpal tunnel syndrome
- Rheumatologic conditions

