### **3.6 Statistical Analysis**

We are planning a study of a continuous response variable from independent control and experimental subjects with 1.1538 control(s) per experimental subject. In a previous study the response within each subject group was normally distributed with standard deviation 0.3. If the true difference in the experimental and control means is 0.2, we will need to study 34 experimental subjects and 39 control subjects to be able to reject the null hypothesis that the population means of the experimental and control groups are equal with probability (power) 0.8. The Type I error probability associated with this test of this null hypothesis is 0.05.

Demographic data and adverse events will be assessed with the chi-square analysis.

Pain scores will be assessed with the Manny-Whitney U test.

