## 8. Appendix

|           |  |
|-----------|--|
| Grade I   | Pain/history of catching                                 |
| Grade II  | Demonstrable catching, but can actively extend the digit |
| Grade III | Demonstrable locking, requiring passive extension        |
| Grade IV  | Fixed flexion contracture                                |

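### No pain score is taken before the injection, so existing finger pain stays in the 1-minute VAS as noise and a chance imbalance in it cannot be seen or adjusted for

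*Combined protocol and SAP*

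**What the plan says.** The aim in Section 2 is to learn whether leaving out lidocaine with epinephrine "decreases pain of the shot without decreasing the effectiveness of the treatment". Pain is measured once. The Abstract states: "The pain levels will be assessed at 1 minute after the injection using the VAS pain scale". Section 3.2 has the matching item, "Reported Pain Score at 1 minute". No section lists a score taken before the needle.

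The Introduction says of the condition: "This can cause pain and dysfunction". The severity table in the Appendix describes Grade I as "Pain/history of catching", but the grade is not among the data points in Section 3.2 either. Eligibility in Section 3.5 does not restrict existing pain.

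The pain analysis in Section 3.6 is one sentence: "Pain scores will be assessed with the Manny-Whitney U test". Comorbid conditions are recorded, but no adjusted model is named.

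**The concern.** The quantity of interest is the pain that the injection causes. A single score one minute later may also reflect how sore the finger already was, which can differ from patient to patient and has nothing to do with the syringe contents. Without a score from just before the injection, that variation stays in the outcome.

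Two things are at stake. The first is precision: if pre-injection pain predicts the 1-minute score, adjusting for it raises power at the same sample size. The second is chance imbalance: with arms of 34 and 39, existing pain can differ noticeably between them by luck. As planned, nobody could see this or adjust for it, and a pre-injection score cannot be collected afterwards.

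**Working it through.** **Inputs.** Section 3.6 gives the SD ("the response within each subject group was normally distributed with standard deviation 0.3"), the difference ("If the true difference in the experimental and control means is 0.2"), 34 experimental and 39 control subjects, power 0.8 and type I error 0.05. It does not state whether the test is one- or two-sided. The correlation r between pre-injection and 1-minute VAS within arms is not in the documents, so it is assumed over a range.

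**1. The plan's own figure.** For a two-sided t-test the standardised difference is 0.2/0.3 = 0.667. The standard error in SD units is √(1/34 + 1/39) = 0.235. The noncentrality is 0.667/0.235 = 2.84 on 71 df, which gives power 0.800. Solving for sample size at the stated ratio of 1.1538 gives 33.9 + 39.1, so the stated 34 + 39 reproduces. A one-sided test would need only 26 experimental subjects and does not match.

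**2. The planned test.** The figure above is for a t-test, but the plan names a Mann-Whitney test. Simulating that test under the same normal assumptions gives power of about 0.78. This is the right comparator for a rank-based adjustment.

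**3. Adjusting for a pre-injection score.** Linear adjustment multiplies the residual variance by 1 − r². Estimating one covariate, and allowing for chance imbalance in it, costs a factor of about 1 − 1/72 and one degree of freedom. The effective standardised difference is

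0.667 × √[(1 − 1/72)/(1 − r²)], on 70 df.

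For example, at r = 0.5 it is 0.667 × √(0.986/0.75) = 0.764, the noncentrality is 0.764/0.235 = 3.26, and power is 0.895. The rank-based figures come from simulation.

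| Assumed r | Linear ANCOVA | Rank-based ANCOVA |
|---|---|---|
| 0 | 0.795 | 0.78 |
| 0.1 | 0.799 | – |
| 0.2 | 0.81 | – |
| 0.3 | 0.83 | 0.81 |
| 0.5 | 0.895 | 0.87 |
| *No adjustment* | *0.80 (t-test)* | *0.78 (Mann-Whitney)* |

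Linear ANCOVA breaks even with the unadjusted t-test at r of about 0.12. Below that it loses at most 0.800 − 0.795 = 0.005.

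**4. Chance imbalance.** The difference in mean pre-injection pain between arms has a standard error of 0.235 baseline SDs. An imbalance larger than 0.3 SD in either direction lies beyond 0.3/0.235 = 1.28 standard errors, which has a probability of about 20%. At an assumed r of 0.5, a 0.3 SD imbalance moves the unadjusted difference by 0.5 × 0.3 × 0.3 = 0.045. That is 0.045/0.2 = 22.5% of the planned effect.

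**The case against.** A reader might infer that existing pain confounds the comparison. The documents do not support that. Section 3.1 gives every patient an equal chance of either syringe and blinds patient and physician. Existing pain is therefore balanced in expectation, and the test's type I error already allows for chance imbalance.

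A reader might also infer that the trial is underpowered because the baseline is missing. That is not supported either. If the SD of 0.3 describes an unadjusted post-injection score, the noise from existing pain is already in it and 34 + 39 gives the stated power. Section 3.6 does not say which outcome or scale the 0.3 and 0.2 refer to, so this can be neither confirmed nor refuted.

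The strongest remaining objection is that r may be small. The Introduction ties symptoms to catching during movement, and Grades II to IV in the Appendix are defined by catching, locking or contracture rather than pain. Pain at rest just before the needle might be low and predict little. At r = 0.2 or below, linear ANCOVA gains about one percentage point or less. The VAS form itself (Appendix Item 2) cannot be seen in the text available. If it asks only about pain from the injection, less existing pain enters the score, though there would still be no baseline.

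All of this stands, and it limits the point to precision and to handling chance imbalance. It does not remove the point, because the possible loss from adjusting is very small beside the gain at moderate r.

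**Conclusion.** The point holds as a cheap improvement in precision, not as a defect in validity. The unadjusted comparison is unbiased, and the stated sample size reproduces. What the plan forgoes is the chance to remove noise from existing pain and to see and adjust for an imbalance in it.

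Against the planned Mann-Whitney test, rank-based adjustment gains about 3 percentage points of power at r = 0.3 (0.78 to 0.81) and about 9 at r = 0.5 (0.78 to 0.87). Setting linear ANCOVA beside Mann-Whitney would credit the baseline with some gain that comes only from changing the test, so each method is compared with its own unadjusted counterpart. All figures assume normal scores, a two-sided 0.05 level, the plan's 0.2 and 0.3, and a value of r that the documents do not supply.

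**What to change.** In Section 3.2, add a VAS mark made by the patient immediately before the injection, on the same scale as the 1-minute score.

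In Section 3.6, prespecify one baseline-adjusted comparison of the 1-minute VAS. A rank-based ANCOVA or a proportional-odds model with pre-injection VAS as covariate stays closest to the planned test. A linear ANCOVA with robust standard errors is also acceptable, but the rank test need not be given up to obtain most of the gain. Report the unadjusted Mann-Whitney test alongside.

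Both changes are needed, since collecting the score does nothing for an unadjusted Mann-Whitney test. A simple change score is not a substitute: if the two scores have equal SDs its variance is 2(1 − r) times that of the 1-minute score, which is larger whenever r is below 0.5.

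The cost is one extra mark per patient at the same visit and a sentence or two in the analysis section. Sample size and visits are unchanged. If r turns out to be below about 0.12, the price is half a percentage point of power or less. The change should be made before enrolment starts.

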## **4. Adverse Reporting**

Adverse events will be reported to the IRB immediately through standard reporting mechanisms. The attending surgeon will be involved with the post-care along with any necessary physician staff.

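### The adverse-effect data item names nothing specific to lidocaine with epinephrine, the only component that differs between arms, so the planned adverse-event comparison may miss harms of that component other than injection pain.

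*Combined protocol and SAP*

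**What the plan says.** - **The arms.** Section 3.1 describes two pre-filled syringes. One holds 1 mL of 1% lidocaine "with epinephrine and 1ml of Kenalog 40 (2 mL total"). The other holds "1mL of 0.9% saline and 1ml of Kenalog 40 (2 mL total"). Steroid and total volume are the same; only the second millilitre differs.
- **The safety data.** The list of data points in section 3.2 has a single entry on harms: "Adverse effects of injection (infection, skin pigmentation, atrophy"). It gives no assessment time and no field for other events, and does not say whether the three effects are a complete list or examples. Type of injection is recorded for each patient.
- **The analysis.** Section 3.6: "Demographic data and adverse events will be assessed with the chi-square analysis". No adverse-event rate or power is stated.
- **Reporting.** Section 4: "Adverse events will be reported to the IRB immediately through standard reporting mechanisms". This is not limited to the three named effects.
- **The one unwanted effect that the documents ascribe to the differing component.** The Abstract says: "Lidocaine with epinephrine is associated with a burning sensation and may be the primary pain associated with the injection". Pain is measured for that purpose: "The pain levels will be assessed at 1 minute after the injection using the VAS pain scale".

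**The concern.** A comparison of adverse events between randomised arms informs about the component that differs only if the events recorded are ones that component could cause. Here the component is lidocaine with epinephrine, and the recorded list contains nothing aimed at it. Staff who follow section 3.2 as written would not be prompted to ask about a faint, palpitations, an allergic reaction or pallor of the digit. If such events occurred, they would reach the analysis only when somebody chose to volunteer or report them.

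What is at stake is how the safety result is read. A finding of no difference in adverse events could be taken as evidence about lidocaine with epinephrine when its own possible effects, beyond pain, had not been systematically sought. The Introduction gives use of fewer drugs as one attraction of the saline arm, so readers are likely to ask this question.

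**Working it through.** **Step 1. Match the recorded effects to the treatment difference.**

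| Item | Lidocaine arm | Saline arm | Recorded as |
|---|---|---|---|
| Kenalog 40, 1 mL | yes | yes | – |
| Total volume 2 mL | yes | yes | – |
| Lidocaine with epinephrine, 1 mL | yes | no (saline) | – |
| Burning or pain on injection | sought | sought | VAS at 1 minute |
| Infection, skin pigmentation, atrophy | sought | sought | section 3.2 item |
| Any other reaction | not solicited | not solicited | IRB report only (section 4) |

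The last row is the gap. An IRB report is made when an event is noticed. It does not supply a yes or no for every patient, which a table by arm needs.

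**Step 2. Reproduce the plan's own figure.** Section 3.6 gives a difference of 0.2, SD 0.3, power 0.8, alpha 0.05 and 1.1538 controls per experimental subject, and concludes that "we will need to study 34 experimental subjects and 39 control subjects". With a two-sided test (sidedness is not stated), the noncentrality is 0.2 / (0.3 × √(1/34 + 1/39)) = 2.84 on 71 degrees of freedom, and power is 0.800. The 34 and 39 reproduce. They were chosen for pain and carry no provision for adverse events.

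**Step 3. What that sample could show if such a harm were recorded.** The documents give no adverse-event rates, so these are assumptions: true rate p with lidocaine and epinephrine, 0 with saline. Section 3.6 does not say which injection is the control, so both assignments are shown.

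With x events among n₁ patients and none among n₂ (N = n₁ + n₂ = 73), the uncorrected statistic is χ² = N·x·n₂ / [n₁·(N − x)], to be compared with 3.84.

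- n₁ = 39, n₂ = 34: x = 4 gives 73 × 4 × 34 / (39 × 69) = 3.69; x = 5 gives 73 × 5 × 34 / (39 × 68) = 4.68. Five events are needed.
- n₁ = 34, n₂ = 39: x = 3 gives 73 × 3 × 39 / (34 × 70) = 3.59; x = 4 gives 73 × 4 × 39 / (34 × 69) = 4.85. Four events are needed.

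Power is then the binomial probability of reaching that count, and the chance of seeing at least one event is 1 − (1 − p)^n₁:

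| Assumed p | Power, n₁ = 39 | Power, n₁ = 34 | At least one event, n₁ = 39 / 34 |
|---|---|---|---|
| 1% | <0.1% | <0.1% | 32% / 29% |
| 2% | 0.1% | 0.5% | 55% / 50% |
| 5% | 4% | 9% | 86% / 82% |
| 10% | 35% | 45% | 98% / 97% |
| 15% | 72% | 77% | >99% / >99% |
| 20% | 91% | 93% | >99% / >99% |

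**Step 4. What zero events would mean.** The one-sided 95% upper bound on the rate is 1 − 0.05^(1/n): 7.4% for n = 39 and 8.4% for n = 34.

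So a reaction with a 5% rate would probably occur at least once and could be described if it were recorded, but the test would rarely flag it.

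**The case against.** The other side has a good deal to say.

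- **The list may be only illustrative.** Sections 3.6 and 4 speak of adverse events without restriction, and any reported event could be assigned to an arm through the recorded injection type. This stands as a limit on the claim: the plan may miss such harms, but the text does not show that it must. It does not remove the gap, because an illustrative list still leaves staff without a prompt for anything else and capture would be uneven.
- **The documented effect is already compared.** Burning is the one unwanted effect that the documents attribute to lidocaine with epinephrine, and the 1-minute VAS covers it. This stands, and the point is confined to other harms.
- **Safety is not a stated objective.** Section 2 aims at pain and effectiveness, and sections 3.1 and 3.3 call both injections standard of care. That lowers the stakes. But section 3.6 does plan an adverse-event analysis, and it should be able to inform about the treatment difference.
- **Recording more would not rescue the test.** Correct, as the power table shows. The gain is in description.

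A reader might go further and infer that all three listed effects come from the shared steroid or needle, so that a null safety result is almost guaranteed. The documents do not support this. They do not trace pigmentation or atrophy to the steroid, and a shared cause would not prove equal rates between arms. Nor is the chance of at least one event a chance of detecting a difference: at an assumed 5% the first is 82% to 86%, the second 4% to 9%.

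**Conclusion.** The concern holds in a limited form. As written, section 3.2 solicits nothing specific to the only component that differs, so the adverse-event comparison in section 3.6 may miss harms of lidocaine with epinephrine other than injection pain. Its size cannot be taken from the documents, which give no event rates. Under the assumed rates, the planned 34 and 39 patients would give under 10% power at 5% versus 0%, and would pass 70% only at about 15% versus 0%. A non-significant chi-square would therefore say little about equal safety, with or without a wider list.

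The conclusion rests on section 3.2 being the working list for data collection. The reactions suggested below are clinical examples, not taken from the documents, and the investigators should confirm them. This is an inexpensive improvement to data capture and reporting; it does not affect the validity of the pain comparison.

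**What to change.** **Section 3.2.** Replace the single adverse-effect item with three parts and state when each is assessed:

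1. Immediate reactions, yes or no for every patient, completed after the VAS is marked and before the patient leaves clinic: for example faint or light-headedness, palpitations, allergic reaction, pallor of the injected digit. Expected numbness while in clinic is not counted as an adverse effect, since it is what a local anaesthetic is meant to produce.
2. Infection, skin pigmentation and atrophy, at a stated time, where possible assessed by someone who did not complete the immediate checklist.
3. Other adverse effects, free text.

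**Section 3.6.** Report immediate and later events separately by arm, as counts with exact confidence intervals. State that a non-significant chi-square will not be interpreted as evidence of equal safety.

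**Cost.** About a minute of staff time per patient at the existing visit. The checklist may reveal the arm to whoever completes it. Placing it after the VAS protects the pain score, and a separate assessor limits the effect on later events. No dose, schedule or treatment changes.

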### **3.3 Study Risk**

This study is categorized as less than minimal risk. We are comparing two treatment methods that are accepted as standard of care, and are already used on the clinic population being studied on a daily basis. There is no new experimental intervention that would put patients at greater than minimal risk

To minimize procedural risks, an experienced clinician will perform all injections. A standardized procedure will also be used for each injection. There will be a timeout before each procedure to

ensure all information is correct and accurate. The skin surrounding the injection site will be throughout cleaned with rubbing alcohol to minimize the risk of infection.

### **3.4 Informed Consent Procedures**

Informed consent will be obtained before performing any procedures. The Principle Investigator or Co-investigator will be obtaining informed consent. All study personnel have successfully completed human subjects training.

### **3.5 Inclusion/Exclusion Criteria**

Inclusion Criteria:

- >18 years

Exclusion Criteria:

- Unconsentable
- Not a candidate for injections

### **3.6 Statistical Analysis**

We are planning a study of a continuous response variable from independent control and experimental subjects with 1.1538 control(s) per experimental subject. In a previous study the response within each subject group was normally distributed with standard deviation 0.3. If the true difference in the experimental and control means is 0.2, we will need to study 34 experimental subjects and 39 control subjects to be able to reject the null hypothesis that the population means of the experimental and control groups are equal with probability (power) 0.8. The Type I error probability associated with this test of this null hypothesis is 0.05.

Demographic data and adverse events will be assessed with the chi-square analysis.

Pain scores will be assessed with the Manny-Whitney U test.

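### Do the unitless SD of 0.3 and difference of 0.2 undermine the 80% power claimed for the VAS pain score?

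*Combined protocol and SAP*

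**What the plan says.** The Abstract names the pain outcome: "The pain levels will be assessed at 1 minute after the injection using the VAS pain scale". Section 3.2 lists that score among the data to be collected. Apart from age, it is the only measurement there that could serve as a continuous response.

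Section 3.6 does not mention the VAS in its power statement. It refers to a continuous response that was normal in each group of a previous study, and gives the two inputs together: "with standard deviation 0.3. If the true difference in the experimental and control means is 0.2". With 34 experimental and 39 control patients, the trial is said to "reject the null hypothesis that the population means of the experimental and control groups are equal" with power 0.8. On the error rate it says: "The Type I error probability associated with this test of this null hypothesis is 0.05". The section gives no unit for 0.2 or 0.3 and does not identify the previous study. Pain scores are to be compared with the Mann-Whitney test.

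The Appendix has an item for the VAS, but only its title is readable in the copy reviewed. The range of the scale therefore cannot be confirmed either way.

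**The concern.** Read as points on a 0–10 scale, an SD of 0.3 means that about 90% of patients in an arm score within half a point of the arm mean. On a 0–100 mm scale it would be a fraction of a millimetre. Either looks too tight for pain after an injection. The unidentified previous study adds to the doubt, because the Abstract says of the two injection methods: "Comparison of these two methods has not been done previously".

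If the true SD were several times larger, 73 patients would have little chance of detecting a 0.2-point difference. A reader who took 0.2 literally might then treat a non-significant result as excluding even a trivial difference, when the trial can reliably detect only a moderate-to-large one. This paragraph is the plan's only justification of its sample size.

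**Working it through.** **Inputs from Section 3.6.** Difference 0.2; SD 0.3; alpha 0.05; power 0.80; 34 experimental and 39 control patients. The section does not say whether the test is one- or two-sided. A two-sided test reproduces the stated numbers; a one-sided test would need only 26 and 30.

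**Step 1: the plan's own figure.** For a two-sample t-test the noncentrality is

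λ = (difference / SD) / √(1/39 + 1/34).

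- √(1/39 + 1/34) = √(0.02564 + 0.02941) = 0.2346
- 0.2 / 0.3 = 0.6667
- λ = 0.6667 / 0.2346 = 2.84, on 39 + 34 − 2 = 71 degrees of freedom

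The noncentral t power is 0.800 (normal approximation 0.811). The stated figure is correct for its inputs.

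**Step 2: what the calculation depends on.** Only the ratio of difference to SD enters λ. Solving for 80% power at 39 and 34 gives 0.666 SD, in whatever unit the response is recorded.

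**Step 3: points on a 0–10 scale.** The documents give no SD for the VAS, so the SDs above 0.3 below are assumptions.

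| SD (points) | Power for a 0.2 difference | Difference with 80% power |
|---|---|---|
| 0.3 (plan) | 80% | 0.20 |
| 1 | 13% | 0.67 |
| 1.5 | 9% | 1.00 |
| 2 | 7% | 1.33 |
| 2.5 | 6% | 1.67 |
| 3 | 6% | 2.00 |

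On an assumed 0–100 scale with SD 10 to 30, power for 0.2 is about 5%, and the difference with 80% power is 6.7 to 20.

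**Step 4: fractions of full scale.** SD 0.3 and difference 0.2 become 0.3 × 10 = 3 and 0.2 × 10 = 2 on a 0–10 scale. The ratio is still 0.667 and the power still 0.800. Normality could only be approximate here: with the mean at mid-scale, a normal curve with SD 0.3 puts P(|Z| > 0.5/0.3) = 0.096 outside the range 0 to 1. The planned rank test does not require normality.

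**Step 5: the planned test.** With the usual 0.955 efficiency of the Mann-Whitney test under normality, power on the normal approximation falls from 0.811 to 0.793. The change of test does not alter the picture.

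**Step 6: whole-number scoring.** Rounding a response with SD 0.3 to whole points gives simulated Mann-Whitney power of about 41–62%, depending on where the mean sits. That does not test the plan's inputs. With the mean on a whole number, about 0.096 of scores move by one point, so the recorded SD is √0.096 = 0.31. With the mean midway between two whole numbers, scores split evenly and the SD is √(0.5 × 0.5) = 0.50. The recorded mean difference also drifts, to between 0.14 and 0.26. The plan does not say that scores are whole numbers, and Section 3.6 treats the response as continuous.

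**The case for a change.** The strongest case for acting is that the paragraph leaves a tenfold ambiguity. The target is either 0.2 or 2 points on a 0–10 scale, and nothing in Section 3.6 says which. Even if the Appendix item printed the range of the scale, it would not supply the source of the SD or the unit of 0.2. Restating the paragraph would cost a few words and no patients.

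The description of the gap stands: outcome, unit and source are all absent, so power for pain in VAS points cannot be verified from the documents. Three further claims do not stand.

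- **That the inputs do not fit a VAS.** Showing this needs a VAS spread, and the documents give none. On the fraction-of-scale reading the inputs fit and the stated power holds.
- **That no reading gives 80% power for a 0.2 difference.** If the SD really is 0.3 points, 0.667 SD is 0.2 points. The plan itself never attaches points to 0.2.
- **That the Abstract contradicts the use of a previous study.** An SD can come from a study of a different comparison. Novelty of this comparison does not rule that out.

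The feared misreading of a null result is also conjecture. What a finished trial can exclude depends on the data observed and their spread, not on the planning SD.

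**Conclusion.** No change to the plan is called for. The power statement is thinly described, but no error in it has been shown. For its own inputs it is right (t-test power 0.800 at 34 and 39), and it is best read as 80% power for a standardized difference of 0.67 SD. An analyst can recover that from the paragraph and, once the trial's SD is known, convert it to VAS points by multiplying the two.

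The figures of 6–13% power require an assumed 0–10 scale, assumed SDs of 1 to 3 points, and a literal reading of 0.2 as points. None of these is in the documents. A restated paragraph would still need an SD and a target in VAS points that the documents cannot supply, and it would leave the sample size, the alpha level, the Mann-Whitney test and the trial's results as they are. This is missing detail in a sample-size justification. A documented VAS SD well above 0.3 on the recorded scale, together with a declared target of 0.2 on that same scale, would change this conclusion; neither is available here.

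### Section 3.6 sizes the trial for 1.1538 controls per experimental patient (34 and 39), but section 3.1 randomizes with equal chance; the ratio and group sizes need correcting, while the total of 73 is not materially wrong.

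*Combined protocol and SAP*

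**What the plan says.** Section 3.6 (Statistical Analysis) describes a comparison of "independent control and experimental subjects with 1.1538 control(s) per experimental subject". It assumes a difference in means of 0.2 and a within-group standard deviation of 0.3, with power 0.8 and a Type I error of 0.05. It concludes that "we will need to study 34 experimental subjects and 39 control subjects", which is 73 in total.

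Section 3.1 (Study Design) states the allocation: "Patients will have an equal (50% chance) of receiving either injection that will be determined by using randomizer software".

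The Abstract only numbers the arms: "The two groups will include (1) 1mL corticosteroid + 1mL Lidocaine with epinephrine vs (2) 1mL corticosteroid + 1mL saline". Section 3.1 numbers them in the same order and describes both as standard of care. Patient groups are called control and experimental only in section 3.6, where the terms are not tied to an injection.

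On the analysis, section 3.6 says: "Pain scores will be assessed with the Manny-Whitney U test".

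**The concern.** A ratio given to four decimals is an input to a calculation, not a rounded form of 1:1. Section 3.6 therefore plans one allocation and section 3.1 another. Whoever sets up the randomization software can program equal chance or 1.1538:1, but not both. Whoever reads the 34 and 39 as targets cannot tell which injection is meant to have the larger group.

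What is at stake is the consistency of the plan and how its size will later be reported. The check below asks whether the mismatch also makes the total or the power wrong.

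**Working it through.** **Inputs, all from section 3.6:** difference 0.2; SD 0.3; alpha 0.05; target power 0.8; ratio 1.1538; group sizes 34 and 39. Section 3.1 supplies the competing 1:1 allocation. Sidedness is not stated, so I took two-sided and tested that choice in step 1.

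**Step 1. Reproduce the plan's figure.**

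- Normal approximation: n(experimental) = (1 + 1/1.1538) × (0.3 × (1.960 + 0.842) / 0.2)² = 32.97, so 33, with 33 × 1.1538 = 38.1 controls.
- Exact two-sided t-test: the smallest experimental group reaching 0.8 is 34, with 34 × 1.1538 = 39.2 controls. This matches 34 and 39.
- A one-sided 0.05 test gives 26 and 30 by the normal approximation, which does not match.

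The stated figures are therefore arithmetically right for a two-sided t-test at 1.1538:1.

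**Step 2. Power at equal allocation on the same inputs.** The standard error is 0.3 × √(1/n₁ + 1/n₂), the noncentrality is 0.2 / SE, and power is the probability that a noncentral t on n₁ + n₂ − 2 degrees of freedom exceeds the two-sided 5% critical value in absolute size.

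| Split | Total | SE | Noncentrality | t-test power |
|---|---|---|---|---|
| 34/39 | 73 | 0.0704 | 2.841 | 0.8003 |
| 36/36 | 72 | 0.0707 | 2.828 | 0.7966 |
| 36/37 | 73 | 0.0702 | 2.848 | 0.8021 |
| 37/37 | 74 | 0.0697 | 2.867 | 0.8076 |

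A 1:1 plan reaches 0.8 at 73 patients split 36/37, or at 74 if the groups must be exactly equal. With 72 it falls just short.

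**Step 3. Allow for chance imbalance.** The document names only randomizer software. If that means simple unrestricted randomization (an assumption), the group sizes at 73 patients vary by chance. Weighting the t-test power of each split by its Binomial(73, 0.5) probability gives an average of 0.797.

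**Step 4. Power for the test the plan names.** Power was simulated for the Mann-Whitney U test with normal data, a standardized difference of 0.2/0.3, the two-sided normal approximation with continuity correction, and 100,000 trials per setting. The results were about 0.78 at 34/39, 0.78 at 36/37, and 0.785 to 0.787 (about 0.79) at 37/37. The simulation error is about √(0.78 × 0.22 / 100,000) = 0.0013. These values sit just below 0.8 and hold only for normal data. With other distributions the power may be higher or lower.

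**The case against.** The strongest reply is that almost nothing depends on the discrepancy. Two-sided t-test power is the same whichever arm has 39, and 73 patients split 36/37 do slightly better than 34/39. Uneven groups are also ordinary under simple equal-chance randomization: at 73 patients a split at least as unequal as 34/39 occurs about 64% of the time. The purpose in section 2 is to see what happens when lidocaine with epinephrine is removed, so the saline arm is the natural experimental arm.

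Most of this stands, and it limits the point to a minor one. It does not remove the contradiction. Section 3.6 states a planned ratio and required group sizes, not a split that might occur by chance, and 1.1538 cannot be the planned ratio of an equal-chance design. The identity of the control arm can be inferred but is nowhere stated.

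Three stronger readings are tempting and are not supported:

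- *The sample size is wrong, or the trial is underpowered because of the ratio.* Step 2 shows that the total fits a 1:1 plan.
- *An equal plan would save patients.* It needs 73 or 74, so the same number or one more.
- *Recruitment will overrun while both group targets are pursued.* No section says that recruitment continues until each group reaches its target.

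A reader may also note that section 3.6 gives 0.2 and 0.3 without a unit and does not identify the previous study. Those are separate reporting points and add no weight here. The outcome can be inferred from "Reported Pain Score at 1 minute" in section 3.2, and Appendix Item 2 may have shown the scale.

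**Conclusion.** The point holds as a minor inconsistency, with high confidence. The ratio and per-group sizes in section 3.6 belong to a 1.1538:1 design, while section 3.1 describes 1:1, and the control injection is not identified. The effect of the ratio on t-test power is about 0.002 at the same total (0.8021 against 0.8003). The validity of the comparison is not affected.

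The stated power of 0.8 belongs to a t-test of means. For the planned Mann-Whitney U test on the same inputs it is about 0.78 to 0.79. That small shortfall comes from the choice of test and not from the allocation ratio.

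These conclusions assume a two-sided 0.05 test, which is the reading that reproduces 34 and 39, and the plan's values of 0.2 and 0.3. The Mann-Whitney figures also assume normal data.

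**What to change.** In section 3.6, replace the 1.1538 ratio and the 34 and 39 with 1:1 allocation and one of two sizes: 36 and 37 (73 in total) or 37 per group (74 in total). Say which injection is the control. If unequal allocation was intended, keep the ratio, change the equal-chance sentence in section 3.1 instead, and say which injection receives 39.

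In the same edit, state power for the planned analysis and label each figure by its test. Suggested content: *Allocation is 1:1. With 37 patients per group, a difference of 0.2 and SD 0.3, the Mann-Whitney U test at two-sided 0.05 has power of about 0.79 if the data are normal; the corresponding t-test power is 0.81.* For 36/37 the figures are about 0.78 and 0.80.

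The cost is two or three sentences, a slightly less favourable stated power, and at most one more patient (74 against 73). Visits, data collection and the test do not change. If a larger control group was wanted for a reason the document does not give, a 1:1 plan gives that up.
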